Abbreviations and Definitions of Terms.....	4
Protocol Synopsis	5
1 BACKGROUND AND RATIONALE	9
2 STUDY OBJECTIVES.....	13
3 INVESTIGATIONAL PLAN.....	13
5 STUDY EVALUATIONS AND MEASUREMENTS.....	18
6 STATISTICAL CONSIDERATION.....	21
7 STUDY PROCEDURES	24
8 DATA COLLECTION AND MANAGEMENT	24
9 CONSENT PROCESS.....	Error! Bookmark not defined.
10 MANAGEMENT AND REPORTING OF ADVERSE EVENTS/ADVERSE REACTIONS	26
11 REFERENCES	28
16 APPENDIX	31

Abbreviations and Definitions of Terms

Abbreviation	Definition
AE	Adverse Event
CAT	COPD Assessment Test
COPD	Chronic obstructive pulmonary disease
DPI	Dry Powdered Inhaler
FEV1	Forced expiratory volume in 1 second
FVC	Forced vital capacity
MDI	Metered dose Inhaler
mMRC	modified Medical Research Council
mBorg	modified Borg dyspnea scale
PIFR	Peak inspiratory flow rate
PRO	Patient reported outcome
RV	Residual Volume
sPIFR	Suboptimal peak inspiratory flow rate

Protocol Synopsis

Study Title	Peak Inspiratory Flow Rate in COPD Patients
Study Rationale	Recent studies have reported that some COPD patients may have a suboptimal ability to generate a sufficient inspiratory effort to achieve adequate lung delivery of inhaled medications through dry powder inhalers. Sparse data is available about the inspiratory capacity of these patients in the home setting, whether clinically stable or when experiencing worsened respiratory symptoms outside the acute care setting. Thus, we are undertaking this study to better understand the proportion of patients with suboptimal peak inspiratory flow rate (sPIFR) measurements amongst COPD patients receiving dry powder inhaler(s) (DPI) in the ambulatory setting. Further, we seek to characterize PIFR over time, the variability of PIFR measurements, and the associations with potential predictors (demographics, clinical, PRO, body position, and device) as well as exacerbations frequency and change in PIFR around period of exacerbation.

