Disease related factors that could affect a patient's inspiratory ability include diaphragmatic dysfunction, air trapping, narrowing of the airways, and worsening respiratory symptoms such as during an exacerbation. (Broeder, Jansenns, Malmberg, Taube, Loh, Sharma). In COPD patients with air trapping, it was shown that in addition to a reduced forced residual capacity and decreased inspiratory capacity, the inspiratory flow was also reduced. (Taube) Decreased inspiratory flow has been shown when COPD patients are clinically stable ([name], Janssen, Mahler, Seheult) and during exacerbations requiring hospitalization. (Broeder, Loh, Sharma) Studies by Loh and Sharma found that impaired PIFR, below minimums for DPIs, occurred in a third or more of COPD patients with acute exacerbations requiring hospitalization. The study by Loh indicated patients with impaired PIFR were at a greater risk of all cause 90-day re-hospitalization, whereas this was not found in the study by Sharma. In the study by Loh, the PIFR was performed in patients while in a sitting position. (personal communication) The decrease in inspiratory flow and capacity apparently persists for some time after exacerbations. Broeder reported that PIFR, using the InCheck DIAL®, increased between 17% and 22% between hospital admission and 5 weeks later when patients were clinically stable in the outpatient setting. There are no published studies that

have measured longitudinal changes in PIFR in ambulatory COPD patients when clinically stable and during periods of worsened respiratory symptoms and recovery.

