4 STUDY PROCEDURES

4.1 Home Monitoring

Subjects will record their PIFR using the InCheck DIAL® and modified Borg dyspnea score three times weekly (MWF) when clinically stable and daily while respiratory symptoms worsen per patient self-assessment. At each session, the participant will repeat efforts three times, with the highest of the three repeated efforts being recorded by the participant. They will be asked to perform the PIFR for the DPI(s) they are receiving at home (Ellipta®, Inhub®, Diskus® or Handihaler®) using the InCheck DIAL®. If on more than one DPI, patient will record PIFR for each device. PIFR will be recorded with best approximation to nearest 1 L/min.

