6 STATISTICAL CONSIDERATION

6.1 Primary Endpoint

For each patient the occurrence of suboptimal Peak Inspiratory Flow Rate (sPIFR) over 24 weeks. sPIFR will be defined as any two consecutive measurements on different days below the optimal threshold for any prescribed DPI (e.g., <30 L/min for Handihaler® (High resistance DPI), <60 L/min for Ellipta® (Medium resistance DPI))

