6.2 Exploratory Endpoints

PIFR Endpoints:

1. Time to first occurrence of sPIFR (in days)
2. Number and proportion of sPIFR
3. Rate of sPIFR, defined as the number of sPIFR / number of days in the study, multiplied by 30 as sPIFR/month.

Exacerbation Endpoints:

Occurrence (yes/no), number, severity (mild, moderate, severe) and rate of COPD exacerbations over 24 weeks. Mild, moderate and severe exacerbations will be defined as:

1. Mild – doubling use of inhaled rescue medication > 48 hours and not meeting definition of moderate or severe
2. Moderate – increased rescue medication and either oral corticosteroid or antibiotics, not requiring hospitalization
3. Severe – hospitalization for exacerbation

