- We will use mixed models to explore associations of monthly PIFR averages over time and clinical and demographic factors. Subjects will be considered as random factor, other variables will be considered fixed effects.
- Association of PIFR with CAT score, mBORG score and mMRC
 - Association of PIFR and CAT scores at V1, V3, V4, V5, V6 (for PIFR, use the measurement in the week of each telephone follow-up, or the month average)

- Correlation of change in CAT scores with change in PIFR from baseline after 24 weeks
- Association of PIFR and mBORG score at V2, V3, V4, V5, V6
- Association of PIFR and mMRC scores at V1, V3, V4, V5, V6 (for PIFR, use the measurement in the week of each telephone follow-up, or the month average)

For COPD exacerbation analyses, the proportion of patients with COPD exacerbations (from Kaplan Meier curve) and the rate of exacerbations occurring during follow-up will be reported along with 95% CI. A patient will be considered censored for exacerbations at the time of the last documented visit, the end of the study, the switching of device (between medium and high resistance DPI) or death (whichever occurs earlier), if they did not experience an exacerbation before. The exacerbations will be reported overall and stratified by severity. The associations between exacerbations and PIFR will be explored in different ways, for all exacerbation, stratified by severity of exacerbations, and stratified by device.

- The rate of exacerbations and sPIFR will be analyzed with negative binomial models (or another model if more appropriate).
- For patients with exacerbations, the mean of PIFR in the week before, of, and after each exacerbation will be calculated and reported.

All tests with p value < 0.05 will be interpreted nominally as statistically significant.

Missing data

- No imputation for PIFR
- No imputation for COPD exacerbations
- No imputation for CAT, mBORG and mMRC

Sample Size and Power

In this application, we propose to recruit 120 COPD participants for study enrollment. There are several rationales for this sample size selection.

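### The exacerbation–sPIFR rate model has no stated outcome and no time order, so exacerbations that lower PIFR can produce a positive association by themselves

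*Combined protocol and SAP*

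**What the plan says.** The rate model is one sentence in section 6.3: "The rate of exacerbations and sPIFR will be analyzed with negative binomial models (or another model if more appropriate". It assigns no outcome or predictor and gives no lag, offset or exclusion of days around an exacerbation.

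Section 6.2 gives both quantities the same window. The sPIFR rate is "Rate of sPIFR, defined as the number of sPIFR / number of days in the study, multiplied by 30 as sPIFR/month", and exacerbations are recorded as "Occurrence (yes/no), number, severity (mild, moderate, severe) and rate of COPD exacerbations over 24 weeks". An sPIFR event is "any two consecutive measurements on different days below the optimal threshold for any prescribed DPI" (section 6.1). Home readings are taken "three times weekly (MWF) when clinically stable and daily while respiratory symptoms worsen per patient self-assessment" (section 4.1).

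Section 1.3 describes the opposite direction of effect: "The decrease in inspiratory flow and capacity apparently persists for some time after exacerbations". It cites a study in which PIFR "increased between 17% and 22% between hospital admission and 5 weeks later when patients were clinically stable in the outpatient setting". The Study Rationale in the synopsis lists among its aims associations with possible predictors, "as well as exacerbations frequency and change in PIFR around period of exacerbation".

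The only planned exacerbation analysis with a time order is a summary of mean PIFR in the weeks before, during and after each event, in patients who exacerbate.

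**The concern.** Every participant enters at or above the device threshold. If an exacerbation lowers PIFR for some weeks, patients with modest reserve can record two consecutive low readings because they exacerbated. Those sPIFR events then enter the same model as the exacerbation that produced them. Taking readings daily during worsening adds chances of a consecutive low pair at that time.

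The resulting rate ratio mixes two questions: whether patients with low PIFR exacerbate more, and whether PIFR falls when patients exacerbate. The second is an objective of the study and has its own summary. The first is how a rate ratio from this model is likely to be read, particularly as section 6.3 calls p < 0.05 nominally significant and section 1.3 cites a study linking impaired PIFR to re-hospitalisation.

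**Working it through.** **The plan's own figure.** No power or effect size is given for this model. The only calculation in the plan is the precision table for the primary proportion, n = 1.96² p(1−p)/h². For p = 0.40 and h = 0.088 this is 3.8415 × 0.24 / 0.007744 = 119.1, rounded up to 120. All 15 cells reproduce, and none bears on this point.

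**Size of the drop.** If PIFR rises by 17–22% from admission to the stable state, PIFR at admission is 1/1.17 to 1/1.22 of the stable value. The drop is 1 − 1/1.17 = 14.5% to 1 − 1/1.22 = 18.0%.

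**Reserve at entry.** The pilot values in section 1.3 are 61 ± 13 L/min (medium resistance) and 36 ± 10 L/min (high resistance). Assuming normality and truncating at the entry limits (60–90 and 30–90) gives means of about 70 and 41 L/min. A patient falls below threshold at the low point if the stable value is under 60 × 1.17 = 70.2 to 60 × 1.22 = 73.2 (medium), or 30 × 1.17 = 35.1 to 30 × 1.22 = 36.6 (high). That is 56–69% of medium-resistance and 26–34% of high-resistance entrants.

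**Null simulation.** PIFR has no effect on exacerbations in any run.

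- From the documents: 60 patients per cohort, 24 weeks (168 days), thresholds of 30 and 60 L/min, the sPIFR definition, and readings on Monday, Wednesday and Friday.
- Assumed, because the documents do not give them: 1 exacerbation per patient-year (120 × 168/365.25 ≈ 55 events), gamma frailty variance 0.5, within-patient SD 3 L/min, linear recovery over 35 days, and, where used, daily readings for 14 days from onset.
- Model: negative binomial for exacerbation count on any sPIFR versus none, adjusted for cohort, two-sided 5% level.

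The first column is from 500 trials per scenario; the second is from a separate simulation.

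| Drop at onset | With daily readings: rate ratio (% significant) | MWF readings only: rate ratio (% significant) |
|---|---|---|
| 0% | 1.00 (3%) | 1.00 (2.5%) |
| 5% | 1.27 (15%) | 1.15 (4.5%) |
| 10% | 1.80 (43%) | 1.45 (19%) |
| 14.5% | 2.32 (77%) | 1.89 (52%) |
| 18% | 2.90 (94%) | 2.32 (80%) |

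**Sensitivity** at a 14.5% drop, with daily readings unless stated:

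| Change | Rate ratio (% significant) |
|---|---|
| 0.5 exacerbations per year | 2.73 (66%) |
| 1.5 exacerbations per year | 2.05 (80%) |
| Within-patient SD 2 | 2.76 (90%) |
| Within-patient SD 5 | 1.90 (55%) |
| 14-day recovery | 2.01 (58%) |
| Frailty variance 1.0 | 2.40 (70%) |
| No extra daily readings | 2.04 (62%) |

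With sPIFR per month as predictor, the rate ratio per SD is 1.41 (89%) at a 14.5% drop and 1.52 (99%) at 18%.

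**Alternatives under the same null.**

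- Enrolment PIFR relative to threshold: rate ratio 0.99–1.01, with 4–6% significant; in the second simulation about 0.9–1.06, with 2.5–6%.
- sPIFR as a share of eligible reading pairs, excluding 7 days before to 35 days after each onset: 0.95–0.99 per SD, with 1–4% significant.
- Simply dropping the readings around exacerbations, without allowing for eligible days: about 0.88. Patients who exacerbate then have fewer days on which sPIFR can be recorded, so the bias turns mildly downward.

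**The case against.** The plan names no outcome and claims no causal direction. It speaks of associations, calls them exploratory, promises to look at them in several ways and allows another model. If sPIFR were the outcome, sPIFR brought on by exacerbations would be the effect sought, and an association that arises this way is a true one. The timing summary is a separate bullet. The 17–22% comes from patients admitted to hospital, whereas the study also counts mild and moderate events; section 1.3 hedges its statement on persistence and says that no published study has followed PIFR longitudinally in ambulatory patients.

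Most of this stands, and it limits the point. A reader might infer that the plan treats sPIFR as a cause of exacerbations; the text does not say so. A reader might also infer that patients enter just above threshold; entry extends up to 90 L/min and the implied means are about 70 and 41. Simulating 120 patients on one medium-resistance device with SD 1.8 L/min gives rate ratios of 3.3–5.4, but the plan recruits 60 per cohort and nothing in it supports so small an SD for home readings (section 1.3 gives a device repeatability of 5 L/min).

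None of this puts a time order into the rate model. The option of another model names no alternative and no trigger. The before/during/after means are descriptive, cover only patients who exacerbate, and do not enter the model.

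**Conclusion.** The point holds as a gap in specification with a predictable direction of bias. As written, the model cannot distinguish sPIFR preceding exacerbations from exacerbations producing sPIFR, and it tends towards a positive association when only the second is true. The simulated rate ratio was above 1 at every non-zero drop tested.

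The size is conditional. Under the base assumptions the null rate ratio is about 1.15–1.3 at a 5% drop, 1.5–1.8 at 10% and 1.9–2.9 at 14.5–18%, nominally significant in about 5–15%, 20–45% and 50–95% of null trials. It is smaller with noisier readings. The ambulatory drop, the exacerbation rate and the within-patient SD are all unknown, so the documents do not support saying that a significant association is bound to appear. The primary endpoint and the sample size are unaffected. The change should be made before analysis, but it concerns an exploratory result.

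**What to change.** In section 6.3:

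1. Name exacerbation count as the outcome, with log follow-up time as offset.
2. Use enrolment PIFR relative to the device threshold as the main predictor.
3. As a supporting analysis, use a time-updated sPIFR status built only from readings before each onset and outside the recovery period of any earlier exacerbation. Account for the number of eligible days, because simply deleting readings biases the result downward.
4. Treat the exclusion window as a sensitivity choice, for example 2 to 5 weeks after onset, with and without the week before onset. The documents fix neither length.
5. Still report the same-window association, labelled concurrent and not interpreted as sPIFR predicting exacerbations.
6. Keep the weekly PIFR means around each event as the analysis of PIFR change with exacerbation.

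This needs SAP wording and some extra programming on data already to be collected. The price is fewer sPIFR events in the lagged predictor, and so less precision.

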2 STUDY OBJECTIVES

2.1 Objectives:

- The primary objective of the study is to determine the proportion of patients with suboptimal peak inspiratory flow rate (sPIFR) measurements amongst COPD patients receiving dry powder inhaler(s) (DPI) in the ambulatory setting.
- The exploratory objectives are to characterize PIFR over time, the variability of PIFR measurements, and the associations with potential predictors (demographics, clinical, PRO, body position, device)
- Additionally, we will explore the exacerbations frequency and change in PIFR around period of exacerbation.

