5.1.4.1 Efficacy Evaluation (if applicable)

Changes in PIFR and dyspnea (modified Borg) that occur in the COPD population in the home setting during periods of stable respiratory symptoms and periods of worsening will be measured and recorded by participating subjects. PIFR measurements, PRO (mMRC, modified Borg, CAT) will also be undertaken in the research clinic setting. PRO will also be completed with each telephone-based study visit.

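### PIFR around exacerbations is summarised in three adjacent weeks with no stable reference and no later window, so the drop may be understated and full recovery cannot be shown

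*Combined protocol and SAP*

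**What the plan says.** Section 2.1 sets the objective: "we will explore the exacerbations frequency and change in PIFR around period of exacerbation". The one specified summary of PIFR level around an event is in Section 6.3, where "the mean of PIFR in the week before, of, and after each exacerbation will be calculated and reported". Section 6.3 does not define the day that anchors these weeks, does not state a contrast between them, and names no stable-period comparator.

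Section 1.3 gives the background. It states: "The decrease in inspiratory flow and capacity apparently persists for some time after exacerbations". It then cites a study in which PIFR "increased between 17% and 22% between hospital admission and 5 weeks later when patients were clinically stable in the outpatient setting". It says no published study has followed PIFR in ambulatory patients "when clinically stable and during periods of worsened respiratory symptoms and recovery".

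The data to fill that gap are planned. Section 4.1 has patients record PIFR "three times weekly (MWF) when clinically stable and daily while respiratory symptoms worsen per patient self-assessment". Section 5.1.4.1 says that changes in PIFR and dyspnea "in the home setting during periods of stable respiratory symptoms and periods of worsening will be measured and recorded", but no analysis in Section 6.3 compares the two kinds of period.

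**The concern.** A change needs a starting level. In a three-week display the week before serves as that level by default. If PIFR has begun to fall before the exacerbation is declared, that week is not a stable reference and the fall into the week of onset looks smaller than it is. The window also closes about two weeks after onset, while the only recovery figure the protocol cites was measured at 5 weeks. A reader of the three means could not tell a patient who is back to normal from one who is still well below it.

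What is at stake is the answer to an exploratory objective and to the gap the protocol itself describes: stable state, worsening and recovery. A small movement across three adjacent weeks could be taken as little effect of exacerbations on inspiratory flow when the design of the summary contributed to it.

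**Working it through.** The plan gives no sample size or precision for this analysis. Its only derived figures are those in the sample-size table for the primary proportion. All 15 cells reproduce with n = 1.96² × p(1−p)/d², rounded up (p = 0.40, d = 0.088 gives 120), and nothing below depends on them.

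**Inputs from the documents (Section 1.3).** Rise r = 17% to 22% from admission to 5 weeks, in hospitalised patients. Pilot means in stable patients: 65 L/min at the first visit for low-medium resistance, 38 L/min for high resistance.

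**Assumptions, not in the documents.** The low point is day 0. The week of onset is days 0-6, the week after is days 7-13 and the week before is days −7 to −1. The cited rise is complete at day 35. The shapes of decline and recovery are varied below.

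**Step 1: deficit implied by the cited rise.** Deficit as a share of the stable level = 1 − 1/(1+r), which is 14.5% for r = 0.17 and 18.0% for r = 0.22.
- At 65 L/min: 9.4 to 11.7 L/min.
- At 38 L/min: 5.5 to 6.9 L/min.

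**Step 2: recovery visible in the planned weeks.** Let R(t) be the share of the deficit recovered by day t. Linear: R(t) = t/35. Exponential: R(t) = (1 − e^(−kt))/q with k = −ln(1−q)/35, scaled so that R(35) = 1; a larger q means earlier recovery.

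| Recovery curve | Mean R, week of | Mean R, week after | Difference |
|---|---|---|---|
| Linear | 0.086 | 0.286 | 0.200 |
| Exponential, q = 0.80 | 0.156 | 0.457 | 0.301 |
| Exponential, q = 0.90 | 0.191 | 0.531 | 0.340 |
| Exponential, q = 0.95 | 0.226 | 0.599 | 0.373 |
| Exponential, q = 0.99 | 0.306 | 0.730 | 0.424 |

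The week-after minus week-of difference therefore shows 20% of the deficit (linear) or 30-42% (exponential):
- At 65 L/min: 1.9-2.3 L/min (linear), up to 4.0-5.0 L/min (q = 0.99).
- At 38 L/min: 1.1-1.4 L/min (linear), up to 2.3-2.9 L/min (q = 0.99).

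The week-after mean would still be short of stable by 71% of the deficit (1 − 0.286) on the linear curve and 27% (1 − 0.730) on the fastest.

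**Step 3: drop visible in the planned weeks.** Let f be the mean share of the deficit already present in the week before. For a linear decline over the L days before onset, f is the average of max(0, (L−d)/L) over d = 1 to 7. The share of the drop shown by week-before minus week-of is (1 − mean R in week of) − f.

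| Decline before onset | f | Shown, linear recovery | Shown, exponential q = 0.99 |
|---|---|---|---|
| None | 0 | 91% | 69% |
| 3 days | 0.143 | 77% | 55% |
| 7 days | 0.429 | 49% | 27% |
| 14 days | 0.714 | 20% | about −2% (no drop) |

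With a 7-day decline and linear recovery, the drop shown is 4.6-5.7 L/min at 65 and 2.7-3.3 L/min at 38.

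**Step 4: cost of a longer window.** Onsets in the last 5 of 24 weeks lack a full 5-week follow-up: 5/24 = 21% of follow-up time.

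**The case against.** The strongest reply is that no bias has been demonstrated. No section reports PIFR in the week before an exacerbation, and more frequent readings when symptoms worsen say nothing about flow. If that week is stable, it is the patient's own reference, and only the averaging of early recovery into the week of onset remains (9% on the linear curve). The 5-week figure is the time of a second measurement, not a demonstrated recovery time; recovery may have finished sooner. It comes from hospital admissions, while this study also counts mild and moderate events. The plan states no week-to-week contrast; it reports three means. Section 6.3 also plans PIFR summaries over time per patient and device, allows individual curves and weekly or monthly summaries, and leaves the exacerbation-PIFR association open to several approaches.

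Most of this stands. A reader might infer that the plan will understate the drop, that all three weeks are depressed, or that most of the recovery will be missed. The documents do not support any of these as fact. Measured from the low point, the week-after mean itself contains 29% to 73% of the recovery, depending on the assumed curve.

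What does not stand is the suggestion that the other analyses close the gap. None defines a stable reference or a recovery window, and the individual curves and the weekly or monthly summaries are optional. The uncertainty about decline and recovery is itself a reason to widen the display, because three adjacent weeks cannot resolve it.

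**Conclusion.** The point holds as a gap in an exploratory analysis. The specified summary has no patient-specific stable level and ends well before the 5-week point the protocol cites. It may understate the drop, by an amount that runs from small to more than half depending on an assumed decline before onset. It cannot show whether recovery is complete. If the cited rise applies, the quantity to be detected is 9.4-11.7 L/min (low-medium resistance) or 5.5-6.9 L/min (high resistance), of which the last two planned weeks would show about 20% to 42% as recovery.

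These sizes rest on hospital data applied to all events, pilot means as the stable level, a low point on day 0 and assumed curve shapes. Milder events may differ.

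**What to change.** Keep the three planned weeks and add the following to Section 6.3:
- **Anchor.** Define the onset day of an exacerbation and number the weeks from it.
- **Stable reference.** For each patient and device setting, take the mean of home readings outside a stated window around any exacerbation. Five weeks after onset matches the cited interval. The documents offer no basis for the length before onset, so state a choice and vary it in a sensitivity analysis.
- **Fallback.** For early or closely repeated events with no such readings, use for example the enrollment-visit PIFR, and flag it. Section 5.1.4 asks for maximum effort at home but the manufacturer's breathing instruction at visits, so the two are not fully alike. Repeat the analysis without these events.
- **Windows.** Extend weekly means to 5 weeks after onset.
- **Estimate.** Report within-patient differences from the stable mean with 95% CIs from a mixed model with a patient random effect and week relative to onset, by device and by severity. State how overlapping and truncated events are handled.

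The cost is a little more analysis; Section 4.1 already collects the readings. Windows will be incomplete for early, repeat and late events, the last being onsets in about 21% of follow-up time.
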